13.0 APPENDIX (see uploaded supporting documents)	

STUDY SCHEMA

STUDY ABSTRACT

The population of aging cancer survivors and their related healthcare needs are rapidly growing in the United States, necessitating the delivery of high-quality, team-based, patient-centered survivorship care long term. However, the delivery of this continuing care after treatment is complex and involves an increasing number of providers, which often results in uncoordinated, fragmented and/or duplicated care as a result. Promoting team-based, patient-centered continuing care after treatment is currently limited by coordination and communication challenges among providers, a lack of evidence about patients' preferences and expectations for their continuing care and few interventions to support the successful transition from primary treatment to survivorship.

The goal of this project is to pilot test a personalized, web-based navigation tool to support the transition from cancer treatment to survivorship that promotes team-based care. Using breast cancer as a model, this study will pilot test a patient-focused website to improve the quality of continuing care after primary treatment, by promoting the participation of the primary care provider in this care. Completion of this pilot study will inform future versions of the tool, as well as the full evaluation of the tool in a multi-site randomized control trial, with the ultimate goal of promoting team-based care plans for breast cancer survivors and informing policies to improve the quality of ongoing continuing care for cancer patients overall.

STUDY SUMMARY

Title	Patient-centered, team-based continuing care after breast cancer treatment: The ConnectedCancerCare Pilot Study
Phase	Pilot study
Objectives	
Aim 1: To conduct a pilot evaluation to assess the feasibility and acceptability of a patient-centered, web-based navigation tool, ConnectedCancerCare, that supports the transition from breast cancer treatment to survivorship and promotes team-based survivorship care.
 
Aim 1A: To assess the feasibility of recruiting at least 60 and up to 70 women with early-stage breast cancer who are completing primary treatment in the breast oncology clinic to the study.
 
Aim 2A: To assess the acceptability of the CCC website among the 30 women randomized to the CCC intervention group.
 
Aim 2: To explore whether CCC influences patient and provider communication about team-based survivorship care, patient-reported knowledge about team-based survivorship care and follow-up visit scheduling in primary care.
 
Aim 3: To conduct debriefing interviews with participating patients and providers in the intervention group to inform the future evaluation and implementation of the tool.

Study Design	Pilot randomized control trial
Eligibility Criteria	
1. Ability to voluntarily provide written IRB-approved informed consent and communicate satisfactorily with the investigator, to participate fully in the study, and comply with all its requirements.2. Women diagnosed with Stages 0-II breast cancer

	3. Women who are receiving care from a medical oncologist 4. Women who are completing their primary treatment for breast cancer and transitioning into survivorship
Statistical Considerations	As this is a pilot study, we will be primarily assessing whether the recruitment of at least 60 and up to 70 women is feasible, and whether the majority of participants (50%) report the tool is acceptable using descriptive statistics. We will assess differences in patient-reported outcomes between the intervention group and control group, but this is an exploratory analysis to guide future versions of the tool and our planned multi-site RCT. As such, a sample size of at least 60 women and up to 70 participants is sufficient to address our primary outcomes (see power calculation section).
Number of Participants	At least 60 and up to 70 women (30-35 intervention and 30-35 control arm)
Estimated Enrollment Period	9 months
Estimated Study Duration	12 months

1. Objectives/Specific Aims

The population of cancer survivors is expected to grow to nearly 19 million by 2024. Breast cancer makes up the largest proportion of cancer survivors (3 million) and most of these patients are over the age of 60 (72%), have survived at least 5 years (89%), and have other medical comorbidities (42%). Nearly all breast cancer survivors will continue to deal with treatment-related issues such as pain, fatigue and lymphedema, and most will also face other comorbid health concerns as they age. This necessitates the delivery of high-quality, team-based, patient-centered continuing care, defined as care that encompasses all aspects of care, not just that related to the breast. However, the quality of continuing care for breast cancer falls short of this goal due to: 1) a burden on patients to coordinate their own care, 2) an increasing number of providers involved in delivering care making coordination and communication more difficult, 3) increasing care fragmentation and duplication of services provided by primary care physicians (PCPs) and oncologists and, importantly, 4) a lack of evidence and interventions to support the successful transition from primary treatment to continuing care.

The National Academy of Medicine’s report on the cancer delivery “system in crisis” calls for comprehensive, patient-centered, team-based continuing care models that promote cross-specialty provider collaboration (particularly between PCPs and oncologists) and decrease patient burden. Yet, providing high quality, team-based care through the transition to survivorship remains a challenge. Although prior research has identified provider-level barriers to providing team-based care, patients’ knowledge of what encompasses continuing care is low, and little is known about patient preferences and expectations for who provides the various aspects of it. Informing patients about team-based continuing care and managing their related expectations is critical to improving care coordination, reducing fragmentation and inefficient use of services. While team-based care models offer promise for improving continuing cancer care, interventions that educate patients about continuing care needs and help them navigate the complexities of their cancer and comorbidity management are needed. Therefore, the goal of this study is to begin to address the existing gaps in the care of breast cancer survivors by building and evaluating an individualized, virtual navigation tool that promotes patient-centered, team-based, continuing care after breast cancer treatment. The specific aims of the study are as follows:

Aim 1: To conduct a pilot evaluation to assess the feasibility and acceptability of a patient-centered, web-based navigation tool, *ConnectedCancerCare*, that supports the transition from breast cancer treatment to survivorship and promotes team-based survivorship care. We will conduct a pilot randomized control trial of our prototype website *ConnectedCancerCare*, which is tailored to patient's knowledge about survivorship care guidelines and their preferences for their oncologist and primary care providers' roles in delivering their survivorship care. We will assess the feasibility of conducting a large-scale RCT in the future and the acceptability of CCC as outlined below in the following sub-aims:

Aim 1A: To assess the feasibility of recruiting at least 60 and up to 70 women with early-stage breast cancer who are completing primary treatment in the breast oncology clinic to the study. We will randomize 30-35 women into the intervention group who will view the CCC website and 30-35 women into the control group, who will view an online care plan document. **H1a:** It will be feasible to deploy CCC in an academic breast clinic, as measured by the successful recruitment of at least 60 and up to 70 women (80%) into the study.

Aim 1B: We will assess the acceptability of the CCC website among the 30-35 women randomized to the CCC intervention group. **H1b:** CCC will demonstrate high usability among those who interact with it, as measured by patient-reported ratings of website usability (ease of use, time to completion, amount of information), usefulness, and whether they would recommend it to others.

Aim 2: To explore whether CCC influences patient and provider communication about team-based survivorship care, patient-reported knowledge about team-based survivorship care and follow-up visit scheduling with primary care. **H2a:** Patients who view CCC will report greater knowledge about and better communication with their providers about team-based survivorship care when compared to the control group. **H2b:** A greater proportion of patients who viewed CCC will report scheduling a follow-up visit with their PCP within 3 months compared to those who viewed the control website.

Aim 3: To conduct debriefing interviews with a sample of patients and their providers about their experiences with *ConnectedCancerCare*. We will debrief oncologists, PCPs and patients (in the intervention arm) about the usefulness of the tool and how to best implement it into practice. The results will then be used to further tailor and revise the tool and develop future evaluation plans, as well as guide post-evaluation implementation and ultimate incorporation into the electronic medical record.

Impact: The findings from this pilot study will directly inform future versions of the CCC intervention and support conducting a full-scale, multi-site, randomized control trial to evaluate whether CCC improves team-based care delivery for breast cancer survivors (planned R01 submission to NCI). More broadly, the findings from this study will also inform future survivorship care delivery strategies and will help guide interventions to improve the delivery and quality of survivorship care, both in breast cancer and other cancers.

2. Background and Significance

The growing number of aging cancer survivors face major challenges because their medical care is especially complex. The population of cancer survivors is expected to approach 19 million by 2024.^{[name]^{1,2}} Breast cancer makes up the largest proportion of survivors (3 million), the majority of which are over the age of 60 (72%) and have survived at least 5 years (89%).¹ Nearly all breast cancer survivors will continue to deal with treatment-

related issues such as pain, fatigue and lymphedema.³⁻⁵ They will also face increasing comorbid health concerns as they age, as 42% have at least one comorbidity,⁶ and on average are seeing 5-16 different doctors.⁷ This obligates the delivery of high-quality, team-based, patient-centered and comprehensive care.

As a result of concerns regarding the quality of cancer care and the rising costs associated with its delivery in the United States, The National Academy of Medicine's (Academy, formerly IOM) released a report in 2013 highlighting the cancer delivery "system in crisis" and calling for comprehensive, patient-centered, team-based continuing care models that promote cross-specialty provider collaboration and decrease patient burden.² The report highlights the explicit goal of providing team-based care to cancer survivors in which members of the cancer team coordinate with primary care to implement care plans and deliver efficient and patient-centered care. Further supporting team-based care models are provisions for patient-centered medical homes and Accountable Care Organizations in the Affordable Care Act, which promote and incentivize a collaborative model of care.⁸ These provisions support oncology providers partnering with primary care and geriatric providers in new ways and integrating primary care into cancer care delivery throughout the continuum of disease.⁹ In addition, one of the conceptual goals of survivorship care plans (SCPs) is to promote collaboration and communication between the providers involved in delivering this care.¹⁰ However, despite high satisfaction among patients, receipt of care plans has been limited,^{11,12} and when evaluated, SCPs were not found to improve care coordination and quality.¹³ Nor have these plans eliminated the patients' confusion around the coordination of team-based continuing care and which provider is delivering it.¹⁴ It is possible that the reason that SCPs have not been successful to date is in part driven by the fact that they are not patient-centered enough, and aren't promoting team-based care as they were intended to do conceptually. Despite these challenges, SCPs have wide support including recommendations from the Academy and the American College of Surgeons Commission on Cancer (ACSCoC). As such, the use of SCPs is starting to be required for ACSCoC cancer program accreditation.¹⁵

Despite these recommendations, policy provisions and the creation of SCPs, it remains very challenging to provide high-quality, patient-centered, team-based care through the transition to survivorship. The often chaotic delivery of cancer care is in part driven by the increasing number of providers involved in delivering the care, the increasing number of comorbid conditions the patients are managing as they age and the burden put on patients to coordinate their ongoing care, often with little support or guidance. Workforce shortages further complicate these issues, as significant shortages in both oncology and primary care physicians are expected by 2020.¹⁶ As patients go through care transitions, such as transitioning from primary treatment to continuing care, they are at increased risk of experiencing fragmented or duplicated care such as repeated or missed clinic visits, lab and imaging tests.¹⁷ Because of these challenges, continuing to provide cancer care without successfully sharing care between specialties such that communication and coordination are improved is not sustainable, and puts the patient at high risk of poor quality outcomes.²

The success of these care models is dependent on understanding the factors that promote or inhibit them. Previous research suggests that primary care physicians (PCPs) and oncologists differ in their knowledge, attitudes and practices as it relates to continuing care.^{18,19} Findings from the Survey of Physician Attitudes Regarding the Care of Cancer Survivors Study (SPARCCS) suggest the majority of oncologists prefer an oncology dominant model of care whereas PCPs prefer a PCP/shared care model.¹⁹ Also, clinicians from both specialties are uncertain about what roles they should play in delivering continuing care, which may lead to duplication or omission of important medical services.¹⁹ While previous studies have identified provider-level barriers to implementing team-based continuing care, there remains a large gap in our understanding about what patients perceive, understand and expect about it. This inhibits

our ability to successfully engage and inform them about their ongoing care needs and sufficiently support them as they complete primary treatment.

To successfully promote team-based continuing care models that are truly patient-centered, we must partner with patients in managing their survivorship care. This requires providing patients with patient-centered, reliable information that helps them to navigate the transition to survivorship and centrally participate in managing their care going forward. Yet, we know very little about patients' preferences and expectations with regard to their continuing care after treatment, particularly as it relates to the role of the PCP. Focus group data suggests that patients feel that their care is in part their responsibility, are open to having PCPs manage aspects of it, but report hesitation and uncertainty about the role that PCPs play in delivering this care.²⁰ As a result, many survivors report that they continue to receive care and reassurance from their cancer specialist rather than their PCP.²⁰ Assessment of patients' attitudes, beliefs and knowledge about team-based continuing care in population-based samples does not currently exist despite qualitative findings that suggest that they may be important barriers to best practices. This lack of understanding hinders our ability to design patient-centered interventions that promote team-based care and improve continuing care quality and coordination. While team-based care models offer promise for improving continuing care, without an understanding of the factors that promote or inhibit them, and the preferences and expectations of those involved, these models will not be effective and our ability to design interventions to promote team-based care will be limited.

Therefore, **the goal of this study is to conduct a pilot evaluation an individualized, virtual navigation tool that promotes patient-centered, team-based, continuing care after breast cancer treatment.** The study objectives address the large gaps in the evidence and the need to develop interventions to improve the quality of collaborative care after cancer treatment. Breast cancer is an excellent model for this work, as the transition from treatment to survivorship is particularly complex with patients remaining on protracted adjuvant therapies. In addition, the findings from this study will also be applicable to other cancer survivors as they transition to survivorship.

3. Preliminary Data

There are untapped opportunities for PCPs to take on a larger role in survivorship care. Our previous findings in the iCanCare Study suggest that PCPs are more involved in care during cancer treatment than previously understood. Most women with early-stage breast cancer reported high primary care quality (as measured by access and relationship with the PCP) during their initial cancer treatment. In addition, the majority reported seeing their current PCP for more than 2 years, and that their PCPs were engaged in and informed about the cancer care they were receiving during treatment. However, almost a quarter of women reported low PCP engagement in and communication about the cancer care during treatment, despite reporting high primary care quality. While our findings suggest PCPs are quite engaged in cancer care during treatment, another recent study from Canada suggests that patient contacts with their PCPs decreased over time in survivorship and were lowest in the adjuvant treatment phase.²¹ Prior work from our group also suggests that PCP involvement may be lower later in survivorship, as only a quarter of women with early-stage breast cancer reported they were followed by a PCP 4 years after diagnosis.²²

There is a need to clarify provider roles during survivorship. Because prior cancer care delivery research has focused on characterizing utilization in survivorship, it remains unknown what aspects of care PCPs are handling vs. what aspects oncologists are handling in survivorship. This has led a lack of clarity regarding provider roles in survivorship care. As a result, current guidelines fall short of clearly delineating which specialty should handle the

various aspects of care. This has led to confusion among both patients and providers.²³ Our prior work in the iCanCare Study supports this, as the majority of women with early-stage breast cancer preferred their oncologists handle multiple aspects of their survivorship care that PCPs typically deliver (e.g. screening for other cancers and comorbidity management).²⁴

In addition, this ongoing lack of clarity about provider roles in survivorship may result in clinicians providing care outside the scope of their specialty. Our preliminary oncologist data from iCanCare suggests that this may be the case, as most medical oncologists reported often having problems in avoiding duplication of care with PCPs as well as coordinating care for existing or new comorbidities. Importantly, over one third of oncologists reported problems even determining whether they or the PCP should provide general preventive care. Others have reported similar findings, specifically with respect to oncologists providing the majority of survivorship care.²⁵ Therefore, oncologists may not only continue to dominate surveillance services and cancer-related follow-up, they may also be delivering aspects of care that PCPs or other specialists typically deliver.

Significant disparities exist in the quality of breast cancer care. Our research group, the Cancer Surveillance and Outcomes Research Team (CanSORT), has extensive experience in conducting population-based studies of diverse cancer patients, their caregivers and clinicians focused on examining disparities in the quality of cancer treatment and outcomes. This work has directly informed multiple patient-level interventions focused on improving the quality of cancer care.²⁶ Our prior research has also demonstrated important sociodemographic disparities in the breast cancer treatment decision-making process²⁷⁻²⁹ and outcomes after treatment,²² including financial toxicity,³⁰⁻³² worry about recurrence³³ and quality of life³⁴ years after initial treatment, notably among black and Latina women.³⁵⁻³⁷ Our population-based research directly informs our intervention research and has led to the development and successful evaluation of a multi-site randomized control trial of a patient decision aid for breast cancer treatment, led by [name] mentor, [name]. The *ConnectedCancerCare* pilot study will be modeled after the pilot approach used to support this study, which ultimately led to the successful recruitment of over 500 patients across multiple clinic sites across the US for the full-scale RCT.³⁸

[figure not shown]
Beta Testing. Usability testing of an early version of the *ConnectedCancerCare* website was conducted with early stage breast cancer patients (n= 4; age range: 33-50 years) who had recently completed active treatment and were in continuing/survivorship care. Patients were identified via outreach with the Breast Cancer Advocacy Committee at UM Rogel Cancer Center. Participants met with a team of developers and designers in the Center for Health Communications Research (CHCR) to go through the website and think out loud about the navigation, flow, usability and drafts of the content. While viewing the beta website on a laptop computer, patients were asked about the ease of navigation and functionality of the site; clarity of links to sections; expectations and satisfaction with information under specific sections; the value of a "to-do" vs. checklist; knowledge of medical team members' roles in their survivorship care; and general questions pertaining to the overall look and feel of the site and what they liked and/or disliked in viewing all the website pages.

Based on their feedback, *ConnectedCancerCare* was enhanced as follows: 1) "to-do" list was combined into the patient checklist and renamed "My Next Steps," 2) information sections were renamed to clarify content (i.e. My primary care doctor became Primary care during survivorship), and 3) greater emphasis was added to onboarding patients and explaining the importance of scheduling a PCP appointment. The modifications made as a result of user testing will provide patients with a better understanding of the primary purpose of the website (i.e. PCP involvement in survivorship care).

Patients also made suggestions for future enhancements to the CCC site which included: expanding the resources section, additional tailoring to specific patient needs, providing a feature to help patients locate a PCP, and integrating the site with the patient portal. These suggestions, combined with feedback we receive from pilot participants who participate in the debriefing interviews, will help inform future enhanced versions of the CCC tool.

4. Methods

Conceptual Model. The overall conceptual model for this study was informed by the Chronic Care Model³⁹ and prior research by our team about treatment decision making, care coordination and the interplay between the health care system, patients and providers during cancer treatment.^{27,28,33,40-42} (Figure 2)

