4.1. Design

The proposed study is a randomized control pilot trial of at least 60 and up to 70 women newly diagnosed with early-stage breast cancer who are finishing primary treatment. Participants will be randomized either to the intervention arm (CCC website that will provide information on team-based follow-up care for both cancer surveillance and preventive care) or the control arm (static online survivorship care plan template which was adapted from the ASCO breast cancer survivorship template). The feasibility and acceptability of the tool and correlations with patient-reported outcomes will be assessed 3 months following the completion of the baseline survey. A sample of 8-10 patients in the intervention arm will then be invited to participate in debriefing interviews to collect feedback regarding their experience with the CCC tool. We will also ask for feedback from 4-6 providers (2-3 medical oncologists and 2-3 PCP's) whose patients participated in the study. Due to time and budget constraints, we are only able to include a sample of patients and providers in our debriefing interviews.

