4.5. Time and Events Table

Study Events	Pre-study (after completing primary treatment)	Time 1 (When viewing the website initially)	Time 2 3 months post-baseline questionnaire completion)	Time 3 1-3 months post-follow-up questionnaire completion)
Informed Consent	X			
Baseline Questionnaire	X			
Randomization		X		
View intervention or control website		X		
Follow-up questionnaire			X	
Debriefing Interviews				X

5. Measures

The measures described in detail below were selected after literature review, and were directly informed by our conceptual model and the results of our prior work and pilot data. The measures are described by specific aim below:

Aim 1A: Feasibility

Feasibility will be defined by the successful recruitment of at least 60 women with half randomized to the intervention website and half to the control website over a 9-month time period. Based upon positive response rates of patients in previous studies of survivorship interventions and the iCanDecide pilot trial, we anticipate approaching approximately 87 women in order to achieve a similar response rate of 80% enrollment (n=70). We will also assess the proportion of those successfully recruited who complete the baseline survey and the follow-up survey. In addition, we will capture paradata including participants' average number of page views, and average time on website.

Aim 1B: Acceptability

Acceptability and usability will be defined by asking participants in the intervention arm to rate their experiences with the tool on 5 point Likert-type scales, as follows: (1) CCC was easy to use, (2) CCC was helpful during my transition to survivorship, (3) CCC helped me think about when to see my PCP and when to see my oncologist, (4) I would recommend CCC to other patients, (5) The time it took to go through the website (6) The amount of info.

Based on our prior work, we will use a cut off of 50% of more reporting a score above 3 as acceptable within that domain. We will also examine the distributions within each domain and determine how we can make the next versions of the tool more acceptable to patients as needed. We will then create a summary score of acceptability by averaging the responses to the 6 items, with a score of 3 or more indicating the tool was acceptable to the majority of patients.

Aim 2: Exploratory patient-reported outcomes

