For pilot testing, the study coordinator will assign a unique study ID to each potential participant. A secure, unique ID access code generated by the website will be used by the participants when they log into the website. Access to the password protected, encrypted, study database will be restricted to the principal investigator and selected members of the study staff. For the physician interviews, the digital recordings and transcripts will also be de-identified and stored in password-protected files, which will only be accessible to the principal investigator and study staff. Patient and provider contact information will be kept in encrypted and password-protected files and used until the study and reporting is completed. The research data, which includes health-related data about the participants collected through the CCC intervention, will be stored for the required 7 years in a secured online server after which time the online data files will be electronically and securely deleted from the server, destroying all data.

Weekly meetings with [name] and the study staff will address any adverse events that could result from pilot study participation (e.g. increased anxiety) and patient and physician interview participation. These are anticipated to be rare and will be handled on an individual basis. Any adverse events will be reported to the IRBMED of the University of Michigan according to current IRBMED reporting guidelines.

7. Data Analysis Plan

Aim 1a: Feasibility

To determine feasibility, we will first assess whether we were successfully able to recruit 80% of our target population (N=87) into the study to achieve a maximum sample size of N=70. We will then generate descriptive statistics of the feasibility measures described above, including % of patients who complete each questionnaire, and average number of page views and time on website.

Aim 1b: Acceptability

The distribution within each of the 5 measures of acceptability will be determined and mean scores >3 within each domain will be examined. For any domain that has a mean score below 3, we will then use that information to inform future adaptations of the tool to increase the acceptability. The distribution of the acceptability summary score of will then be assessed and the proportion of patients with a score of 3 or more will be calculated.

Aim 2: Exploratory Patient-Reported Outcomes

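### Feasibility has two pass marks: at least 60 women within 9 months in Section 5, but 80% of 87 (70 women, the stated maximum) in Section 7

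*Combined protocol and SAP*

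**What the plan says.** Section 5 (Measures, Aim 1A) gives the definition: "Feasibility will be defined by the successful recruitment of at least 60 women with half randomized". It goes on to specify equal allocation between the two sites and a recruitment window of 9 months. The same paragraph then gives a planning figure: "we anticipate approaching approximately 87 women in order to achieve a similar response rate of 80% enrollment (n=70").

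Section 7 (Data Analysis Plan, Aim 1a) gives the analysis: "To determine feasibility, we will first assess whether we were successfully able to recruit 80% of our target population (N=87) into the study". The rest of that sentence ties the 80% to reaching the cap of 70. Neither the figure of 60 nor the 9-month window appears there.

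H1a in Section 1 says that feasibility will be shown "as measured by the successful recruitment of at least 60 and up to 70 women (80%) into the study".

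The Study Summary (Statistical Considerations) says "we will be primarily assessing whether the recruitment of at least 60 and up to 70 women is feasible" and attaches no percentage. Section 4.1 describes a "randomized control pilot trial of at least 60 and up to 70 women", again with none.

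**The concern.** One section says what feasibility is and another says how it will be determined, and the two do not match. Section 5 is a count with a time limit. Section 7 is a rate against a fixed number of women, with no time limit, and its pass mark is the top of the planned enrolment range.

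Recruitment is one of the two things the Study Summary says the pilot primarily assesses, and Aim 1 uses it to judge whether a large-scale randomised trial is feasible. If enrolment ends between 60 and 69 with 87 women approached, the result can be reported as a success under Section 5 or a failure under Section 7. Nothing in the plan says which rule governs, so the choice could be made after the count is known.

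**Working it through.** **Inputs**
- Minimum 60 women, 9 months: Section 5, Aim 1A.
- About 87 approached, 80% enrolment, n = 70: Section 5, Aim 1A.
- 80% of N = 87, maximum N = 70: Section 7, Aim 1a.
- Range 60 to 70, labelled 80%: Section 1, H1a.
- True enrolment rate: not known. Values from 65% to 90% are assumed below for illustration only.

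**Step 1. The plan's own figure.** 0.80 × 87 = 69.6, which rounds up to 70. In reverse, 70 / 0.80 = 87.5, which agrees with about 87. The planning arithmetic reproduces.

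**Step 2. What each rule needs when 87 are approached.**
- Section 5: 60 women, and 60/87 = 69.0%.
- Section 7: 69/87 = 79.3% falls short and 70/87 = 80.5% passes, so 70 women.

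**Step 3. Where the rules part.** The planned range 60 to 70 contains 11 counts. Ten of them (60 to 69) pass Section 5, if reached within 9 months, and miss Section 7. Only 70 passes both.

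**Step 4. H1a.** Against 87, the 80% label fits 70 women and not 60. For 60 women to be 80%, the denominator would have to be 60 / 0.80 = 75, a number the plan does not give.

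**Step 5. How often this could matter.** Let X be the number enrolled out of exactly 87 approached, binomial with true rate p. The rules disagree when 60 ≤ X ≤ 69, so P(disagree) = P(X ≥ 60) − P(X ≥ 70).

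| p | P(X ≥ 60) | P(X ≥ 70) | P(disagree) |
|---|---|---|---|
| 0.65 | 0.256 | 0.001 | 0.25 |
| 0.70 | 0.634 | 0.019 | 0.61 |
| 0.75 | 0.920 | 0.146 | 0.77 |
| 0.80 | 0.995 | 0.521 | 0.47 |
| 0.85 | 1.000 | 0.906 | 0.09 |
| 0.90 | 1.000 | 0.998 | 0.002 |

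At the plan's own 80%, Section 5 is met almost surely and Section 7 about half the time.

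**Step 6. What a count alone leaves out.** Enrolling 60 of 120 approached would meet the Section 5 count at a rate of 50% (exact 95% CI 40.7% to 59.3%). Enrolling 60 of 87 is 69.0% (58.1% to 78.5%), and 70 of 87 is 80.5% (70.6% to 88.2%). The rate carries information for a later trial that the count does not.

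**The case against.** The strongest reply is that 60 is the minimum, 70 the cap, and 80% merely the planning rate that produced 87. Section 5 supports this: it uses the language of definition for 60 and of anticipation for 87. Section 7 calls 70 a maximum and goes on to descriptive statistics. No formal test or go/no-go rule is tied to either figure, so the harm is mainly ambiguous reporting. This is probably what was intended, but it does not remove the conflict, because Section 7 opens by saying that the 80%-of-87 comparison is how feasibility is determined. The monitoring text in Sections 9.2 and 9.3 covers recruitment against expectation, but sets no pass mark and does not reconcile the two rules.

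Other parts of the reply stand and limit the point:
- A reader might infer that H1a is plainly wrong in labelling the whole range 80%. The parenthesis follows the figure 70 and may belong to it alone, as in Section 5. H1a is ambiguous, not demonstrably in error.
- A reader might quote 0.47 as the chance of conflict. That holds only for exactly 87 approached and a true rate of exactly 80%; the plan says approximately 87.
- A reader might infer that Section 7 becomes unattainable under the cap once 88 women are approached (70/88 = 79.5%). Section 7 fixes its denominator at 87, and 79.5% rounds to 80%. If the number actually approached were used instead, 60 of 75 would meet both rules.
- A reader might infer that 87 is too few to give good assurance of success. The plan sets no assurance standard to judge that by.
- A reader might infer that baseline completion must be 100%, because Section 4.2 verifies enrolment by consent plus baseline questionnaire. Section 4.4.4 has women consent first and then follows up those who have not completed the baseline, so non-completion can be observed.

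**Conclusion.** The inconsistency is real and should be fixed. Sections 5 and 7 set different pass marks, 60 and 70, for a primary assessment of the pilot. With 87 women approached they classify every count from 60 to 69 differently. This follows from the text and simple division and needs no assumption about the true enrolment rate. The disagreement probabilities (0.002 to 0.77 for true rates between 65% and 90%) are illustrative. They assume exactly 87 approached and independent decisions with a common enrolment probability.

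The fault lies chiefly in the Section 7 sentence. H1a contributes a percentage without a denominator. The planning arithmetic is sound, and no formal hypothesis test is affected.

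**What to change.** - Use the Section 5 rule, at least 60 women recruited within 9 months, as the single deciding criterion in H1a, Section 5 and Section 7.
- In H1a and Section 7, restate 80% as the planning expectation, with its denominator: 70 of about 87 women approached.
- In Section 7, report the observed enrolment rate (women enrolled divided by eligible women approached) with an exact 95% confidence interval beside the count, and compare it descriptively with the 80% expectation. This keeps the benchmark visible and shows a low rate that a count of 60 could hide.

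The cost is a wording change in H1a and Section 7, plus one added record. Section 4.2 already has the coordinator identify eligible women before the visit, but only those who are interested go on to meet the coordinator. The coordinator would therefore need to record eligible women who decline when the oncologist introduces the study. The sample size, randomisation and questionnaires stay as they are.
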